9.2.1. Serious Adverse Events

An SAE is any AE from this study that results in one of the following:

- death
- initial or prolonged inpatient hospitalization
- a life-threatening experience (that is, immediate risk of dying)
- persistent or significant disability/incapacity
- congenital anomaly/birth defect
- events considered significant by the investigator based upon appropriate medical judgment

Study site personnel must alert Lilly, or its designee, of any SAE within 24 hours of investigator awareness of the event via a sponsor-approved method. If alerts are issued via telephone, they are to be immediately followed with official notification on study-specific SAE forms. This 24-hour notification requirement refers to the initial SAE information and all follow-up SAE information.

Although all AEs are recorded in the eCRF after signing informed consent, SAE reporting begins after the subject has signed informed consent and has received investigational product.

However, if an SAE occurs after signing informed consent, but prior to receiving investigational product, AND is considered reasonably possibly related to a study procedure then it MUST be reported.

Investigators are not obligated to actively seek AEs or SAEs in subjects once they have discontinued from and/or completed the study (the subject summary eCRF has been completed). However, if the investigator learns of any SAE, including a death, at any time after a subject has been discharged from the study, and he/she considers the event reasonably possibly related to the study treatment or study participation, the investigator must promptly notify Lilly .

Pregnancy (maternal or paternal exposure to investigational product) does not meet the definition of an AE. However, to fulfill regulatory requirements any pregnancy should be reported following the SAE process to collect data on the outcome for both mother and fetus.

9.2.1.1. Suspected Unexpected Serious Adverse Reactions

Suspected unexpected serious adverse reactions (SUSARs) are serious events that are not listed in the IB and that the investigator identifies as related to investigational product or procedure. United States 21 Code of Federal Regulations 312.32 and European Union Clinical Trial Directive 2001/20/EC and the associated detailed guidances or national regulatory requirements in participating countries require the reporting of SUSARs. Lilly has procedures that will be followed for the recording and expedited reporting of SUSARs that are consistent with global regulations and the associated detailed guidances.

9.2.2. Complaint Handling

Lilly collects product complaints on investigational products used in clinical trials in order to ensure the safety of study participants, monitor quality, and to facilitate process and product improvements.

Subjects should be instructed to contact the investigator as soon as possible if he or she has a complaint or problem with the investigational product so that the situation can be assessed.

9.3. Treatment of Overdose

For the purposes of this study, an overdose of baricitinib is considered any dose higher than the dose assigned.

The IB contains information on the highest single doses administered to healthy subjects. There is no specific antidote for baricitinib. In the event of an overdose, the subject should receive appropriate supportive care and any AEs should be documented.

9.4. Safety

9.4.1. Laboratory Tests

For each subject, laboratory tests detailed in [Appendix 2](#) should be conducted according to the Schedule of Activities (Section [2](#)).

9.4.2. Vital Signs

For each subject, vital signs measurements should be conducted according to the Schedule of Activities (Section [2](#)).

Blood pressure and pulse rate should be measured after at least 5 minutes supine.

Additional vital signs may be assessed as clinically indicated as well as at the scheduled times. Unscheduled orthostatic vital signs should be assessed, if possible, during any AE of dizziness or posture-induced symptoms. If orthostatic measurements are required, subjects should be supine for at least 5 minutes and stand for at least 3 minutes. If the subject feels unable to stand, supine vital signs only will be recorded.

Additional vital signs may be measured during each study period if warranted and agreed upon between the sponsor and investigator.

9.4.3. Electrocardiograms

For each subject, ECGs should be collected according to the Schedule of Activities (Section [2](#)).

Any clinically significant findings from ECGs that result in a diagnosis and that occur after the subject receives the first dose of the investigational product should be reported to Lilly, or its designee, as an AE via eCRF.

For each subject, a single 12-lead digital ECG will be collected according to the Schedule of Activities (Section [2](#)). Electrocardiograms must be recorded before collecting any blood for

safety or PK tests. Subjects must be supine for approximately 5 to 10 minutes before ECG collection and remain supine but awake during ECG collection. Electrocardiograms may be obtained at additional times, when deemed clinically necessary. All ECGs recorded should be stored at the investigational site.

Electrocardiograms will be interpreted by a qualified physician (the investigator or qualified designee) at the site as soon after the time of ECG collection as possible, and ideally while the subject is still present, to determine whether the subject meets entry criteria at the relevant visit(s) and for immediate subject management, should any clinically relevant findings be identified.

If a clinically significant finding is identified (including, but not limited to, changes in QT/QT corrected for heart rate interval from baseline) after enrollment, the investigator will determine if the subject can continue in the study. The investigator, or qualified designee, is responsible for determining if any change in subject management is needed, and must document his/her review of the ECG printed at the time of collection. Any new clinically relevant finding should be reported as an AE.

9.4.4. Safety Monitoring

The Lilly CP or CRP/clinical research scientist will monitor safety data throughout the course of the study.

Lilly will review SAEs within time frames mandated by company procedures. The Lilly CP or CRP will consult with the functionally independent Global Patient Safety therapeutic area physician or clinical research scientist when appropriate, and periodically review:

- trends in safety data
- laboratory analytes
- AEs

9.5. Pharmacokinetics

At the visits and times specified in the Schedule of Activities (Section 2), venous blood samples of approximately 3 mL each will be collected to determine the plasma concentrations of baricitinib. A maximum of 5 samples may be collected at additional time points during each part of the study if warranted and agreed upon between both the investigator and sponsor.

Instructions for the collection and handling of blood samples will be provided by the sponsor. The actual date and time (24-hour clock time) of each sampling will be recorded.

9.5.1. Bioanalysis

Samples will be analyzed at a laboratory approved by the sponsor and stored at a facility designated by the sponsor.

Concentrations of baricitinib will be assayed using a validated liquid chromatography with tandem mass spectrometric detection method.

Bioanalytical samples collected to measure investigational product concentrations will be retained for a maximum of 1 year following last subject visit for the study.

9.6. Pharmacodynamics

This section is not applicable for this study.

9.7. Genetics

A blood sample will be collected for pharmacogenetic analysis as specified in the Schedule of Activities (Section 2), where local regulations allow.

Samples will not be used to conduct unspecified disease or population genetic research either now or in the future. Samples will be used to investigate variable response to baricitinib and to investigate genetic variants thought to play a role in inflammatory disease. Assessment of variable response may include evaluation of AEs or differences in efficacy.

All samples will be coded with the subject number. These samples and any data generated can be linked back to the subject only by the investigative site personnel.

Samples will be retained for a maximum of 15 years after the last subject visit, or for a shorter period if local regulations and/or ethical review boards (ERBs) impose shorter time limits, for the study at a facility selected by Lilly or its designee. This retention period enables use of new technologies, response to regulatory questions, and investigation of variable response that may not be observed until later in the development of baricitinib or after baricitinib is commercially available.

Molecular technologies are expected to improve during the 15-year storage period and therefore cannot be specifically named. However, existing approaches include whole genome or exome sequencing, genome wide association studies, multiplex assays, and candidate gene studies. Regardless of technology utilized, data generated will be used only for the specific research scope described in this section.

9.8. Biomarkers

This section is not applicable for this study.

9.9. Health Economics

This section is not applicable for this study.

10. Statistical Considerations and Data Analysis

10.1. Sample Size Determination

In Part A, 26 subjects may be enrolled to ensure that 20 complete the study.

For C_{max} , assuming an intra-subject coefficient of variation of 16%, 20 subjects provide 90% power to show bioequivalence for a 95% confidence interval (CI) using 0.8 and 1.25 as the lower and upper bioequivalence limits, respectively. A 95% CI was used to calculate the power for this study to assure both comparisons of the suspension formulation (with and without water) versus the commercial tablet had adequate power using the Holm's step-down procedure. This procedure adjusts for multiplicity maintaining the family-wise type 1 error rate.

For $AUC(0-\infty)$ and $AUC(0-t_{last})$, assuming an intra-subject coefficient of variation of 7.8% and 7.6%, respectively, 20 subjects provide greater than 99% power to show bioequivalence for a 95% CI using 0.8 and 1.25 as the lower and upper bioequivalence limits, respectively.

In Part B, it is planned that up to a maximum of 18 subjects will be enrolled in order that 14 complete the study; however, this number may be revised based on interim analysis of the intra-subject variation in PK parameters of baricitinib suspension formulation in Part A of the study.

Subjects who are randomized and discontinue the study prior to completion of all study periods in their assigned study part may be replaced to ensure that a minimum of 20 subjects complete Part A of the study and 14 complete Part B. Replacement subjects will complete all 3 periods (Part A) or 2 periods (Part B), following the sequence of the withdrawn subject.

10.2. Populations for Analyses

10.2.1. Study Participant Disposition

A detailed description of subject disposition will be provided at the end of the study.

10.2.2. Study Participant Characteristics

The subject's age, sex, weight, height, BMI, race, and other demographic characteristics will be recorded and summarized using descriptive statistics.

10.3.1. Safety Analyses

10.3.1.1. Clinical Evaluation of Safety

All investigational product and protocol procedure AEs will be listed, and if the frequency of events allows, safety data will be summarized using descriptive methodology.

The incidence of symptoms for each treatment will be presented by severity and by association with investigational product as perceived by the investigator. Symptoms reported to occur prior to study entry will be distinguished from those reported as new or increased in severity during the study. Each symptom will be classified by the most suitable term from the medical regulatory dictionary.

The number of investigational product-related SAEs will be reported.

10.3.1.2. Statistical Evaluation of Safety

Safety parameters that will be assessed include TEAEs, clinical laboratory parameters, and vital signs. The parameters will be listed, and summarized using standard descriptive statistics, as appropriate. Additional analysis will be performed if warranted upon review of the data.

10.3.2. Pharmacokinetic Analyses

10.3.2.1. Pharmacokinetic Parameter Estimation

Pharmacokinetic parameter estimates for baricitinib will be calculated by standard noncompartmental methods of analysis.

The primary parameters for analysis will be C_{max} , $AUC(0-t_{last})$, and $AUC(0-\infty)$. The t_{max} will be observed from the data. Other noncompartmental parameters may be reported.

10.3.2.2. Pharmacokinetic Statistical Inference

Pharmacokinetic parameter estimates will be evaluated to delineate effects of baricitinib formulation. For the primary analysis, log-transformed C_{max} , $AUC(0-t_{last})$, and $AUC(0-\infty)$ estimates will be evaluated in a linear mixed-effects model with fixed effects for formulation, period, sequence, and a random effect for subject (sequence). The treatment differences between each test compared to the reference formulation will be back-transformed to present the ratios of geometric least squares means and the corresponding CIs. The Holm step-down procedure for an overall 0.1 alpha level will be used.

Bioequivalence between the suspension formulation administered either with or without water and the commercial tablet will be concluded if the 95% CI for C_{max} , $AUC(0-t_{last})$, and $AUC(0-\infty)$ are all completely contained within the interval (0.80, 1.25). Bioequivalence between the suspension formulation using the other administration and the commercial tablet will be

concluded if the 90% CIs for C_{max} , $AUC(0-t_{last})$, and $AUC(0-\infty)$ are all completely contained within the interval (0.80, 1.25).

For secondary analyses, the same model specified above will be used for C_{max} , $AUC(0-t_{last})$, and $AUC(0-\infty)$. Ratios of geometric least squares means and the corresponding 90% CIs will be presented. The t_{max} will be analyzed using a Wilcoxon signed rank test. Estimates of the median difference based on the observed medians, 90% CIs, and p-values from the Wilcoxon test will be calculated.

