9.3.2 Pharmacokinetic Statistical Methodology

PK parameters will be evaluated to delineate the effects of baricitinib formulation. For the primary analysis, log-transformed C_{max} , $AUC(0-t_{last})$, and $AUC(0-\infty)$ estimates will be evaluated in a linear mixed effects model with fixed effects for formulation, period, sequence, and a random effect for subject (sequence). The treatment differences between each test compared to the reference formulation will be back-transformed to present the ratios of geometric least squares (LS) means and the corresponding CIs. The Holm step-down procedure for an overall 0.1 alpha level will be used. This analysis applies only to Part A.

Bioequivalence between the suspension formulation administered either with or without water and the commercial tablet will be concluded if the 95% CI for C_{max} , $AUC(0-t_{last})$, and $AUC(0-\infty)$ are all completely contained within the interval (0.80, 1.25). If at least one of the administrations has all three 95% CIs contained within the interval (0.8, 1.25), then the second administration will be declared bioequivalent if the 90% CIs for C_{max} , $AUC(0-t_{last})$, and $AUC(0-\infty)$ are all completely contained within the interval (0.80, 1.25). The following comparisons shall be made:

- 4 mg baricitinib suspension with 240 mL water (fasted) vs 4 mg baricitinib tablet with 240 mL water (fasted)
- 4 mg baricitinib suspension without water (fasted) vs 4 mg baricitinib tablet with 240 mL water (fasted)

Example SAS code is provided below.

```
proc mixed data=dataset;
class subject group period sequence;
model l&var=group period sequence / cl solution outpred=resids;
random intercept / subject=subject(sequence);
lsmeans group / pdiff cl;
ods output lsmeans=lsmeans;
ods output diff=diffs;
run;
quit;
```

The same model will be used to compare the relative bioavailability of the suspension formulation administered with (test) and without (reference) water, with a significance level of 0.1. This analysis applies to Part A.

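### Does Holm at an overall alpha of 0.1 contradict the 95%-then-90% confidence interval rule, or overstate the false-bioequivalence rate?

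*Protocol*

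**What the plan says.** The protocol Synopsis, protocol section 10.3.2.2 and SAP section 9.3.2 all carry the same sentence on multiplicity: "The Holm step-down procedure for an overall 0.1 alpha level will be used". None says whether 0.1 is two-sided, one minus interval coverage, or a rate of false bioequivalence claims.

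Each place then sets out the decision rule in interval terms. One administration of the suspension is bioequivalent to the tablet if its 95% intervals for Cmax, AUC(0-tlast) and AUC(0-∞) all lie within 0.80 to 1.25. For the other administration, 90% intervals are enough. SAP section 9.3.2 makes the order explicit: "If at least one of the administrations has all three 95% CIs contained within the interval (0.8, 1.25), then the second administration" is judged on its 90% intervals.

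Protocol section 10.1 (repeated in SAP section 7) ties the sample size to the stricter step: "assuming an intra-subject coefficient of variation of 16%, 20 subjects provide 90% power to show bioequivalence for a 95% confidence interval (CI"). On Holm's method it adds: "This procedure adjusts for multiplicity maintaining the family-wise type 1 error rate". It attaches no number to that rate.

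**The concern.** In a bioequivalence study, the type I error is a claim of equivalence when the true ratio lies outside the limits. Placing a 95% interval inside the limits is the same as two one-sided tests (TOST), each at 0.025. A 90% interval corresponds to 0.05. Holm over two comparisons at 0.025 and then 0.05 has a family-wise error of 0.05, whereas the only overall level the documents state is 0.1.

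Two consequences seem to follow. A reader could conclude that the study accepts a 10% chance of a false claim. An analyst who built Holm from the stated alpha and TOST p-values would test at 0.05 and then 0.10, which means 90% and then 80% intervals. That rule would allow twice the error and conflict with the sentences that follow the alpha statement. If either reading were forced by the text, a headline operating characteristic would be wrong.

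**Working it through.** **Inputs.** Overall alpha 0.1, two comparisons, intervals at 95% then 90% (protocol 10.3.2.2, SAP 9.3.2). Limits 0.80 and 1.25, 20 completers, intra-subject CV 16% for Cmax, and 7.8% and 7.6% for AUC(0-∞) and AUC(0-tlast) (protocol 10.1). The true ratio is not stated, so it was varied.

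**1. The stated alpha on the interval scale.** Holm with two comparisons tests first at alpha/2, then at alpha. With alpha defined as one minus coverage:

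- Step 1: 0.1/2 = 0.05, coverage 1 − 0.05 = 95%.
- Step 2: 0.1/1 = 0.10, coverage 1 − 0.10 = 90%.

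This is the written rule, so the stated figure reproduces.

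**2. The same rule on the TOST scale.** An interval of coverage 1 − 2a corresponds to TOST at level a.

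- 95%: a = 0.025.
- 90%: a = 0.05.

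That is Holm at 0.05. If both administrations are truly non-equivalent, any false claim needs at least one to pass at 0.025, so the error is at most 2 × 0.025 = 0.05. If only one is, it must pass at 0.05 or stricter, so the error is again at most 0.05. Requiring all three PK parameters to pass can only lower this.

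**3. Simulation.** One PK parameter, shared reference, 20 subjects, 36 degrees of freedom (60 observations − 20 subjects − 2 for period − 2 for treatment), 2,000,000 trials per scenario, CV 16% unless noted. The last column shows Holm at 0.1 applied to TOST p-values.

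| True ratios of the two administrations | Written rule (95%/90%) | 90%/80% rule |
|---|---|---|
| 1.25 and 1.25 | 0.045 | 0.087 |
| 1.25 and 0.80 | 0.050 | 0.100 |
| 1.25 and 1.00 | 0.049 | 0.100 |
| 1.25 and 1.05 | 0.050 | 0.100 |
| 1.25 and 1.00, CV 7.8% | 0.050 | 0.100 |

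**4. Power.** For Cmax, the log-scale SD is √ln(1 + 0.16²) = 0.159 and the standard error of a contrast is 0.159 × √(2/20) = 0.0503. TOST power with a 95% interval, using 18 (two-period) or 36 (three-period) degrees of freedom:

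| True ratio | 18 df | 36 df |
|---|---|---|
| 1.00 | 0.974 | 0.982 |
| 1.05 | 0.905 | 0.921 |
| 0.95 | 0.897 | 0.914 |
| 1.06 | 0.872 | 0.891 |

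The stated 90% is recovered at a true ratio of about 0.95 or 1.05. AUC power exceeds 0.999 for ratios from 1.00 to 1.08, in line with the stated value above 99%. The sample size was therefore worked out on the interval scale as well.

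**5. Which scale the documents use.** SAP 9.3.2 sets a significance level of 0.1 for suspension with versus without water, a comparison that protocol 10.3.2.2 reports with 90% intervals. There 0.1 is one minus coverage. SAP 9.3.2 also carries the 95/90% interval pair over to tmax. The only p-values the text plans for PK comparisons come from the Wilcoxon test on tmax.

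**The case for a change.** The best argument for a change is that Holm's method is defined on p-values, that overall type I error is a headline property of a study meant to show definitive equivalence, and that 0.1 is the only overall level given. An unlabelled level can be read in two ways, and one of them has double the error of the other. The SAP's other use of 0.1 does not fully settle the matter: if the with-versus-without-water comparison is taken as a test of difference, 0.1 there is a genuine 10% type I error. The protocol also leaves the order of the two steps implicit, so it leans more on the alpha sentence than the SAP does. A label would cost one sentence in each of three places.

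What stands is that the scale is unlabelled and that a reader has to work out the 0.05. The contradiction does not stand. It appears only once Holm is applied to TOST p-values, a step neither document contains. To arrive at 90% then 80% intervals, an analyst would have to set aside the interval levels written directly after the alpha sentence and, in the SAP, the explicit ordering of the steps. Nor does either document state a 10% false-bioequivalence rate. Calling 0.1 twice the real alpha compares a level on the interval scale with an error rate on the TOST scale.

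**Conclusion.** No change follows. The 0.1 is an interval-scale level without a label. On that scale it gives exactly the 95%-then-90% rule that both documents spell out. Following the rule as written holds the family-wise false-bioequivalence rate to at most 0.05 (0.045 to 0.050 in the scenarios simulated), so the label, if misread, overstates the risk and hides no inflation. Rewording would alter no interval, decision, sample size or power figure, and a statistician running this analysis would apply the stated intervals.

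The 0.05 bound comes from the Holm argument and does not depend on the variance. The simulated values assume equal within-subject variance across treatments, 20 completers and a single PK parameter. The power check also rests on an assumed true ratio, which the documents do not give.

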10.3.3. Interim Analyses

A formal interim analysis will be performed after completion of Part A of the study. This is an open-label study. Pharmacokinetic data will be analyzed after all PK data are available for Part A of the study. Statistical analysis will be conducted to test the baricitinib suspension formulation, administered with and without water, for bioequivalence with the commercial tablet formulation. The administration method for the suspension formulation that is bioequivalent to the commercial tablet formulation will be used in Part B of the study. If both administration methods are bioequivalent to the commercial tablet formulation, suspension will be administered without water in Part B of the study, for ease of administration. If the suspension formulation is not bioequivalent to the commercial tablet formulation using either administration method, all available data will be used to assess the most appropriate way to administer the drug in Part B.

Intra-subject variability estimates of PK parameters will be used to determine the number of subjects required to complete Part B of the study.

11. References

[FDA 2002] US Department of Health and Human Services Food and Drug Administration Center for Drug Evaluation and Research. Guidance for Industry. Food-Effect Bioavailability and Fed Bioequivalence Studies. 2002.

